4.4. End of Study Definition

The end of the study is defined as the date of the last scheduled procedure shown in the [SoA](#) for the last participant in the trial.

A participant is considered to have completed the study if they have completed all periods of the study, including the last scheduled procedure shown in the [SoA](#).

5. STUDY POPULATION

This study can fulfill its objectives only if appropriate participants are enrolled, including participants across diverse and representative racial and ethnic backgrounds. Use of a prescreening tool is utilized for study recruitment purposes, it will include collection of information that reflects the enrollment of a diverse participant population including, where permitted under local regulations, age, sex, and race, and ethnicity. The following eligibility criteria are designed to select participants for whom participation in the study is considered appropriate. All relevant medical and nonmedical conditions should be taken into consideration when deciding whether a particular participant is suitable for this protocol.

Prospective approval of protocol deviations to recruitment and enrollment criteria, also known as protocol waivers or exemptions, is not permitted.

5.1. Inclusion Criteria

Participants are eligible to be included in the study only if all of the following criteria apply:

Age and Sex:

1. Participants ≥ 18 and ≤ 65 years of age, inclusive, at the time of signing the ICD.
Refer to [Appendix 4](#) for reproductive criteria for male ([Section 10.4.1](#)) and female ([Section 10.4.2](#)) participants.
2. Male participants and female participants of non-childbearing potential ([Section 10.4.2](#)) who are overtly healthy as determined by medical evaluation including medical history, physical examination, laboratory tests, vital signs and 12-lead ECGs.

Other Inclusion Criteria:

3. BMI of 17.5 to 30.5 kg/m^2 ; and a total body weight >50 kg (110 lb).
4. Participants who are willing and able to comply with all scheduled visits, treatment plan, laboratory tests, lifestyle considerations, and other study procedures.
5. Capable of giving signed informed consent as described in [Appendix 1](#), which includes compliance with the requirements and restrictions listed in the ICD and in this protocol.

5.2. Exclusion Criteria

Participants are excluded from the study if any of the following criteria apply:

Medical Conditions:

1. Evidence or history of clinically significant uveitis, hematological, renal, endocrine, pulmonary, gastrointestinal, cardiovascular, hepatic, psychiatric, neurological, or allergic disease (including drug allergies, but excluding untreated, asymptomatic, seasonal allergies at the time of dosing).
 - Any condition possibly affecting drug absorption (eg, gastrectomy, cholecystectomy).
 - History of HIV infection, hepatitis B, or hepatitis C; positive testing for HIV, HBsAg, HBcAb or HCVAb. Hepatitis B vaccination is allowed.
 - Use of PPIs is not allowed within 7 days of study start (C1D1) and during study treatment.

2. Other medical or psychiatric condition including recent (within the past year) or active suicidal ideation/behavior or laboratory abnormality or other conditions or situations related to COVID-19 pandemic (eg, contact with positive case, residence, or travel to an area with high incidence) that may increase the risk of study participation or, in the investigator's judgment, make the participant inappropriate for the study.

Prior/Concomitant Therapy:

3. Use of prescription or nonprescription drugs and dietary and herbal supplements within 7 days or 5 half-lives (whichever is longer) prior to the first dose of study intervention. (Refer to Section [6.9](#) Prior and Concomitant Therapy for additional details).
4. Current use or anticipated need for drugs that are known strong UGT2B7 inhibitors, including the administration within 10 days or 5 half-lives, whichever is longer, or strong UGT2B7 inducers, including the administration within 5 half-lives plus 10 days, prior to first dose of PF-07284890. Refer to Section [6.9](#) Prior and Concomitant Therapy and [Appendix 9](#).
5. Participant who have received a COVID-19 vaccine within 7 days before screening or admission, or who are to be vaccinated with a COVID-19 vaccine at any time during the study confinement period.

Prior/Concurrent Clinical Study Experience:

6. Previous administration with an investigational product (drug or vaccine) within 30 days (or as determined by the local requirement) or 5 half-lives preceding the first dose of study intervention used in this study (whichever is longer).

Diagnostic Assessments:

7. Positive test result (RT-PCR) for SARS-CoV-2 infection at the time of screening or Day -1.
8. A positive urine drug test at screening or admission.
9. A positive urine cotinine test at screening or admission.
10. Screening supine BP ≥ 140 mm Hg (systolic) or ≥ 90 mm Hg (diastolic), following at least 5 minutes of supine rest. If BP is ≥ 140 mm Hg (systolic) or ≥ 90 mm Hg (diastolic), the BP should be repeated 2 more times and the average of the 3 BP values should be used to determine the participant's eligibility.
11. Standard 12-lead ECG that demonstrates clinically relevant abnormalities that may affect participant safety or interpretation of study results (eg, QTcF ≥ 450 ms, complete LBBB, signs of an acute or indeterminate- age myocardial infarction, ST-T

interval changes suggestive of myocardial ischemia, second- or third- degree AV block, or serious bradyarrhythmias or tachyarrhythmias). If the uncorrected QT interval is >450 ms, this interval should be rate-corrected using the Fridericia method only and the resulting QTcF should be used for decision making and reporting. If QTcF exceeds 450 ms, or QRS exceeds 120 ms, the ECG should be repeated twice and the average of the 3 QTcF or QRS values used to determine the participant's eligibility. Computer-interpreted ECGs should be overread by a physician experienced in reading ECGs before excluding a participant.

12. Participants with **ANY** of the following abnormalities in clinical laboratory tests at screening, as assessed by the study-specific laboratory and confirmed by a single repeat test, if deemed necessary:
 - AST **or** ALT level $\geq 1.25 \times$ ULN;
 - Total bilirubin level $\geq 1.5 \times$ ULN; participants with a history of Gilbert's syndrome may have direct bilirubin measured and would be eligible for this study provided the direct bilirubin level is \leq ULN.
 - eGFR <75 mL/min/1.73 m² based on the CKD-EPI equation.
 - Hemoglobin <11 g/dL
 - ANC $<1.5 \times 10^9$ /L
 - Platelets $<100,000/\text{mm}^3$

Other Exclusion Criteria:

13. History of alcohol abuse or binge drinking and/or any other illicit drug use or dependence within 6 months of Screening. Binge drinking is defined as a pattern of 5 (male) and 4 (female) or more alcoholic drinks in about 2 hours. As a general rule, alcohol intake should not exceed 14 units per week (1 unit = 8 ounces (240 mL) beer, 1 ounce (30 mL) of 40% spirit, or 3 ounces (90 mL) of wine).
14. Current smokers or history of the use of tobacco- or nicotine-containing products within 6 months of screening.
15. Blood donation (excluding plasma donations) of approximately 1 pint (500 mL) or more within 60 days prior to dosing.
16. History of sensitivity to heparin or heparin-induced thrombocytopenia.
17. Unwilling or unable to comply with the criteria in the [Lifestyle Considerations](#) section of this protocol.

18. Investigator site staff directly involved in the conduct of the study and their family members, site staff otherwise supervised by the investigator, and sponsor and sponsor delegate employees directly involved in the conduct of the study and their family members.

5.3. Lifestyle Considerations

The following guidelines are provided:

5.3.1. Contraception

The investigator or their designee, in consultation with the participant, will confirm that the participant is utilizing an appropriate method of contraception for the individual participant and their partner(s) from the permitted list of contraception methods (see [Appendix 4](#), Section 10.4.4) and will confirm that the participant has been instructed in its consistent and correct use. At time points indicated in [SoA](#), the investigator or designee will inform the participant of the need to use highly effective contraception consistently and correctly and document the conversation and the participant's affirmation in the participant's chart. Participants need to affirm their consistent and correct use of at least 1 of the selected methods of contraception, considering that their risk for pregnancy may have changed since the last visit.

In addition, the investigator or designee will instruct the participant to call immediately if the selected contraception method is discontinued and document the requirement to use an alternate protocol-specified method, including if the participant will no longer use abstinence as the selected contraception method, or if pregnancy is known or suspected in the participant or partner.

5.3.2. Meals and Dietary Restrictions

- Participants must abstain from all food and drink (except water) at least 4 hours prior to any safety laboratory evaluations and 10 hours prior to the collection of the predose PK sample. All 3 periods will have a 10-hour fast, followed by pre-dose ECGs and PK sampling (which will be followed by food in the fed periods, Sequence 2 Period 1 and Sequence 1 Period 2 for the low-fat meal and Period 3 for the high-fat meal, prior to dosing).
- For the fasted period (Sequence 1 Period 1 and Sequence 2 Period 2), water is permitted until 1 hour prior to study intervention administration. Water may be consumed without restriction beginning 1 hour after dosing. Noncaffeinated drinks may be consumed with meals and the evening snack.
- For the first fed period, low-fat meal (Sequence 2 Period 1 and Sequence 1 Period 2 for the low-fat meal) only, a low-fat (approximately 25% of total caloric content of the meal), low-calorie (approximately 400 to 500 calories) meal will be used for the evaluation of a food effect in this study. The provided meal will be similar in composition to the meal referenced in the FDA guidance on food-effect bioavailability and fed bioequivalence studies.¹⁵ On Day 1 of the first fed period,

following an overnight fast of at least 10 hours, participants should begin breakfast approximately 30 minutes prior to PF-07284890 administration. The breakfast will be consumed over approximately a 20-minute interval with PF-07284890 administered within approximately 10 minutes of completion of the meal. Participants will be encouraged to complete the entire breakfast. There are no water restrictions prior to and after dosing.

- For the second fed period, high-fat meal (Period 3) only, a high-fat (approximately 50% of total caloric content of the meal), high-calorie (approximately 800 to 1000 calories) meal will be used for the evaluation of a food effect in this study. The provided meal will be similar in composition to the meal referenced in the FDA guidance on food-effect bioavailability and fed bioequivalence studies.¹⁵ On Day 1 of the fed Period 3, following an overnight fast of at least 10 hours, participants should begin breakfast approximately 30 minutes prior to PF-07284890 administration. The breakfast will be consumed over approximately a 20-minute interval with PF-07284890 administered within approximately 10 minutes of completion of the meal. Participants will be encouraged to complete the entire breakfast. There are no water restrictions prior to and after dosing.
- Lunch will be provided approximately 4 to 5 hours after dosing.
- Dinner will be provided approximately 9 to 10 hours after dosing.
- An evening snack may be permitted.
- While participants are confined, their total daily nutritional composition should be approximately 55% carbohydrate, 30% fat, and 15% protein. The daily caloric intake per participant should not exceed approximately 3200 kcal.

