2.2.2. Nonclinical Pharmacokinetics and Metabolism

After oral administration, plasma exposures of PF-07284890 (AUC and C_{max}) increased with dose in all species and the absolute oral bioavailability was moderate to complete. GLP TK studies in the rat (doses of 10, 30 and 60 mg/kg) and monkey (doses of 10, 30 and 100 mg/kg) showed less than dose-proportional exposures, as might be expected based on relatively low aqueous solubility (ie, in simulated gastric fluid at 37°C at a pH of 1.2, 131.6 µg/mL, and in fasted state simulated intestinal fluid at a pH of 6.5, 7.6 µg/mL).

In vitro and in vivo metabolite identification suggested that PF-07284890 was metabolized through multiple oxidative and/or glucuronosyltransferase enzymes. Comparisons of across species suggested that direct N-glucuronidation is predicted to be the predominant metabolic route in humans. PF-07284890 glucuronidation is the primary route of metabolism in human hepatocytes with minor contribution from CYP3A4 and aldehyde oxidase. An in vitro study conducted to characterize the involvement of 11 selected human UGTs isoforms in the metabolism of PF-07284890 indicated that UGT2B7 was the principal human isoform likely responsible for primary glucuronide conjugates. Renal clearance was a minor elimination route of unchanged PF-07284890 in rats (<1% of an IV dose) and is predicted to be a minor route across all species, including humans.

Additional information of the nonclinical PK and metabolism of PF-07321332 is available in the current IB.

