6.1.1. Administration

Investigational product will be administered orally and according to the conditions described in the [SoA](#) section and Protocol Section [5.3.2 Meals and Dietary Restrictions](#).

For **fasted** period (Sequence 1 Period 1 and Sequence 2 Period 2):

- On Day 1, following an overnight fast of at least 10 hours, the participants will receive 200 mg PF-07284890 (as 2 × 100 mg tablets) administered orally at approximately 08:00 hours (plus or minus 2 hours) without breakfast/standard meal on Day 1.

For **fed** periods (Sequence 2 Period 1 and Sequence 1 Period 2 for the low-fat meal and Period 3 for the high-fat meal):

- On Day 1, following an overnight fast of at least 10 hours, participants will receive breakfast approximately 30 minutes prior to dosing which is to be completed within approximately 20 minutes as outlined in Section [5.3.2 Meals and Dietary Restrictions](#). The participants will then receive 200 mg PF-07284890 (as 2 × 100 mg tablets) administered orally at approximately 08:00 hours (plus or minus 2 hours).

For **all** periods:

- Investigator site personnel will administer study intervention during each period with ambient temperature water to a total volume of approximately 240 mL. Participants will swallow all tablet formulations whole, and will not manipulate or chew the study intervention prior to swallowing.

- In order to standardize the conditions on PK sampling days, all participants will be required to refrain from lying down (except when required for BP, pulse rate, and ECG measurements), eating, and drinking beverages other than water during the first 4 hours after dosing.

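### The rule on drinking water around dosing differs between the fasted period and both fed periods, so each food-effect ratio combines the meal with any effect of a difference in water intake; size and direction are unknown and the remedy is cheap

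*Protocol*

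**What the plan says.** Protocol 5.3.2 (Meals and Dietary Restrictions) sets the water rule separately for each condition.

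- **Fasted, Treatment A (Reference):** "water is permitted until 1 hour prior to study intervention administration. Water may be consumed without restriction beginning 1 hour after dosing".
- **Low-fat, Treatment B, and high-fat, Treatment C:** "There are no water restrictions prior to and after dosing". The sentence appears in both fed bullets.

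Two other rules apply to every period. Protocol 6.1.1 fixes the dosing water: "Investigator site personnel will administer study intervention during each period with ambient temperature water to a total volume of approximately 240 mL". The same section, and Protocol 5.3.4, require participants to refrain from lying down, "eating, and drinking beverages other than water during the first 4 hours after dosing". The purpose given is "In order to standardize the conditions on PK sampling days". That rule leaves plain water open.

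I found no reason stated for the different water rules, and no provision in the Schedule of Activities or elsewhere for recording water intake.

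The primary endpoints (Protocol 3, SAP 3.1) are the ratios of AUClast, AUCinf and Cmax, each fed condition against fasted.

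**The concern.** The two primary objectives concern the effect of a low-fat and of a high-fat meal. For the ratios to be read that way, fasted and fed periods should differ in the meal and in as little else as possible. Here they also differ in permitted water during the 2 hours around dosing, and the volume is left to the participant.

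Water intake could matter for this compound. Protocol 2.2.2 links less than dose-proportional exposure in animals to "relatively low aqueous solubility", and Protocol 4.3 describes a weak base in BCS Class II. The results are meant to inform food instructions for patients in the first-in-patient study (Protocol 2.1, SAP 2), so the ratios should be attributable to food as far as is practical.

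**Working it through.** **Step 1. Set the rules side by side** (Protocol 5.3.2, 5.3.4, 6.1.1).

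| Condition | A, fasted | B, low-fat | C, high-fat |
|---|---|---|---|
| Additional water, last hour before dosing | no | unrestricted | unrestricted |
| Dosing water | about 240 mL | about 240 mL | about 240 mL |
| Additional water, first hour after dosing | no | unrestricted | unrestricted |
| Water from 1 h after dosing | unrestricted | unrestricted | unrestricted |
| Food and other beverages, 0 to 4 h | no | no | no |
| Breakfast begun about 30 min before dosing | none | low-fat | high-fat |

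Apart from the meal, the fasted and fed columns differ in two rows, and both concern water.

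**Step 2. Can the analysis separate them?** Let W = 1 when water is unrestricted around dosing and 0 otherwise. On the log scale, write w_B and w_C for any effect of W. The contrasts then estimate

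- B − A = meal effect (low-fat) + w_B
- C − A = meal effect (high-fat) + w_C

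In the B versus A data W equals the indicator for B; in the C versus A data it equals the indicator for C. The models contain sequence, period and treatment (B versus A) or sequence and treatment (C versus A), with participant within sequence random. None of these terms can pull W apart from treatment. Randomising the order of A and B does not help, because the water rule moves with the meal. B and C share one rule, so a C to B comparison would be free of w if w_B = w_C, but that is not a primary endpoint.

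**Step 3. Reproduce the planned precision** (Protocol 9.5). Inputs: n = 12; within-participant SD 0.3491 (AUC) and 0.3890 (Cmax) on the log scale; 90% interval; 80% coverage probability. Use df = 10, as for a 2-sequence, 2-period crossover.

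Half-width = t(0.95, df) × SD × √(2/n) × √(χ²(0.80, df)/df)

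- AUC: t × SD × √(2/12) = 0.2583; with the χ² factor, 0.2995. The protocol states 0.2995.
- Cmax: 0.2878; with the χ² factor, 0.3337. The protocol states 0.3337.

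Both match.

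**Step 4. Illustrate what a water effect would do.** The documents give no value, so suppose that the water difference multiplies fed exposure by an **assumed** factor f from 1.00 to 1.30. The log bias is ln f. Coverage of the pure meal effect by the 90% interval comes from the noncentral t distribution with df = 10 and noncentrality ln f / (SD × √(2/12)).

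| Assumed f | ln f | Share of planned half-width, AUC / Cmax | Coverage, AUC / Cmax |
|---|---|---|---|
| 1.00 | 0 | 0 / 0 | 90.0% / 90.0% |
| 1.05 | 0.0488 | 16.3% / 14.6% | 88.3% / 88.6% |
| 1.10 | 0.0953 | 31.8% / 28.6% | 83.5% / 84.7% |
| 1.20 | 0.1823 | 60.9% / 54.6% | 67.2% / 71.4% |
| 1.30 | 0.2624 | 87.6% / 78.6% | 47.2% / 54.1% |

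A decrease by the same factor (for example 1/1.10 = 0.91) gives the same coverage, with the bias in the other direction. For scale, a 2-fold food effect is ln 2 = 0.693, so f = 1.10 would be 0.0953/0.693 = 14% of it on the log scale. The table shows what would follow from a given f. It is not evidence that f differs from 1.

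**The case against.** The strongest reply is that the documents show a difference in permission and nothing more. Dosing water is equal in all periods, nobody is required to drink more when fed, and no figure links water volume to AUC or Cmax in humans. From 1 hour after dosing the rules are identical, while median Tmax ranged from 1.5 to 6.0 hours (Protocol 2.2.4.2), so much of absorption may take place under the same conditions. The study tests no hypothesis (Protocol 9.1, SAP 5.1) and sets no equivalence bounds. The meals are tied to a cited guidance not available here, so whether the water rule follows it cannot be judged. A common window would still leave any drink served with the meal as a fluid difference.

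Most of this stands, and it limits the point in two ways.

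- **Direction.** A reader might infer that every participant drinks more when fed and that both ratios are therefore biased one way. The documents do not support this: intake is the participant's choice and no direction of effect is given.
- **Size from solubility.** A reader might infer a size from Protocol 2.2.2. At 131.6 µg/mL (simulated gastric fluid, pH 1.2), 240 mL dissolves 131.6 × 240 = 31.6 mg, or 16% of 200 mg; doubling the volume to 480 mL gives 63.2 mg, or 32%. But 480 mL appears nowhere in the documents, and pH 1.2 fluid does not represent a stomach that has just received a meal. At the other stated value, 7.6 µg/mL (fasted intestinal fluid), the same sums give 1.8 mg (0.9%) and 3.6 mg (1.8%). Neither calculation predicts AUC or Cmax. The solubility remark itself concerns rat and monkey studies.

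What the reply does not remove is the difference in rules. It is unexplained, cannot be removed in the analysis, and sits awkwardly with the protocol's own aim of standardising the sampling days.

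**Conclusion.** The point holds as an avoidable non-meal difference, fully aliased with treatment in both primary ratios. Its existence follows from Protocol 5.3.2 and the model specifications and needs no assumption.

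Its materiality is unproven. Actual intake, and the size and direction of any effect, cannot be derived from the documents. If water intake around dosing turns out alike, or has no effect on exposure, there is no bias. If it changed exposure by 5 to 10%, the bias would be roughly 15 to 32% of the planned half-width, which is modest beside a food effect of up to about 2-fold (Protocol 4.2.1). The planned sample size and precision are not in question. I would not call the food-effect estimates invalid on this ground; I would call the difference a cheap thing to put right.

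**What to change.** Reconcile the bullets in Protocol 5.3.2 so that one water rule around dosing applies in all three periods. The simplest way is to remove the unrestricted-water sentence from both fed bullets and apply the fasted-period window throughout, excepting the approximately 240 mL of dosing water and any drink that is a defined part of the test meal.

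If the sponsor prefers to keep different rules, the protocol should give the reason and require the volume of water taken from 1 hour before to 1 hour after dosing to be recorded in each period, so that any imbalance can at least be described by treatment.

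Cost: two sentences in 5.3.2, and minor inconvenience to participants for about 2 hours in two periods. The common window adds no procedure and changes neither sample size nor model; the planned half-widths stay at 0.2995 and 0.3337. The recording option adds a small data item. Any fluid served with the test meal remains part of the meal effect.
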